2.3 Risk Benefit Assessment

Among AML patients, approximately 30% are refractory to induction therapy and of those who achieve CR, approximately 75% will relapse. Generally, there is no established standard of care for these patients and less than 20% will achieve CR with subsequent treatment. The response duration for patients who achieve CR with subsequent treatment is limited and most patients relapse. Patients who are in second relapse or refractory to first salvage have an extremely poor prognosis, with survival measured in weeks.

For MDS, the currently available treatments are not curative and no standard of care is available for patients after failure to respond to hypomethylating agents [Uy et al, 2017]. Patients with higher-risk disease have an expected median overall survival of less than 2 years. Patients who experience standard treatment failure have median survival of less than 6 months and limited treatment options with consideration given to clinical trials [Sekeres & Culter, 2014].

ASP7517 has effects against WT1 expressing tumors and showed no significant safety findings in the pre-clinical pharmacology studies. In the repeated dose toxicity studies with mice, all major findings were reversible and monitorable and will not interfere with human clinical studies recruiting AML and MDS patients, considering its potential benefit against the risk.

3 STUDY OBJECTIVE(S) AND ENDPOINT(S)

The study objectives and endpoints for this study are provided in [Table 7](#).

Table 7 Study Objectives and Endpoints

Objective(s)	Endpoint(s)
Primary	
• To evaluate the safety and tolerability of ASP7517• To determine the RP2D and/or the MTD of ASP7517 (phase 1)• To evaluate the clinical response of ASP7517 
• Safety and tolerability as noted by: DLTs, AEs, SAEs, laboratory test results (serum, chemistry, hematology, coagulation, and urinalysis, pregnancy test) ECGs, vital signs, physical exams and ECOG performance status scores• CRc rate for subjects with R/R AML and (CR + BM CR + PR) rate for R/R higher risk MDS (phase 2)
Secondary	
• To evaluate other measures of anticancer activity of ASP7517 
• Duration of remission• EFS• OS• CR, best response (CRc + PR) and CRh rates for subjects with R/R AML• CR, HI and objective response (CR + BM CR + PR + HI) rates for subjects with R/R higher risk MDS
Exploratory	
• To evaluate potential genomic, proteomic and/or other biomarkers that may correlate with treatment outcome• To evaluate pharmacodynamic activities of ASP7517• To evaluate pharmacokinetics of ASP7517, which is determined by the kinetics of the cells 
• Exploratory biomarkers that may correlate with treatment outcome of ASP7517• Pharmacodynamic effects of ASP7517, such as changes in:
○ Cytokine expression and secretion (e.g., IFNg)○ WT1-specific T lymphocytes (e.g., cytotoxic T lymphocytes)○ Immune cell populations (NKT cells, NK cells, etc.)• Cellular DNA load and kinetic parameter estimates for ASP7517

AE: adverse event; AML: acute myeloid leukemia; BM: bone marrow; CR: complete remission; CRc: composite complete remission; CRh: complete remission with partial hematologic recovery; DLT: dose limiting toxicity; ECG: electrocardiogram; ECOG: Eastern Cooperative Oncology Group; EFS: event-free survival; IFNg: interferon gamma; HI: hematologic improvement; MDS: myelodysplastic syndrome; MTD: maximum tolerated dose; NK: natural killer; NKT: natural killer T; OS: overall survival; PR: partial remission; R/R: relapsed/refractory; RP2D: recommended phase 2 dose; SAE: serious adverse event; WT1: Wilms' tumor 1 protein.

4 STUDY DESIGN AND DOSE RATIONALE

4.1 Study Design

This study is a phase 1/2, open-label study of ASP7517 (human embryonic kidney cell transfected with encoding target antigen WT1) in subjects with R/R AML and R/R higher risk MDS.

A total of approximately 122 subjects are planned for enrollment in this study.

In phase 1 (Dose Escalation), approximately 18 subjects with either AML or MDS will be enrolled.

In phase 2 (Dose Expansion), approximately 104 subjects will be enrolled per dose level. Each dose level may enroll up to 52 subjects with R/R AML and up to 52 subjects with R/R higher risk MDS. Both groups of subjects will enroll in parallel and independently.

4.1.1 Study Periods

The study consists of the following periods:

- Screening (up to 14 days)
- Treatment (two 28-day cycles during escalation phase; up to six 28-day cycles during expansion phase)
- EoT visit
- Post-Treatment
 - Observation Period 1 (12 weeks or until 1 post-treatment discontinuation criterion is met, whichever occurs first)
 - Observation Period 2 (assessment visit every month until 1 post-treatment discontinuation criterion is met)
- Survival and subsequent treatment follow-up every 3 months

During the treatment period, subjects will receive an intravenous infusion of ASP7517 (human embryonic kidney cell transfected with encoding target antigen WT1).

In phase 1 (dose escalation), subjects will receive 1 dose of ASP7517 per cycle for a total of 2 doses.

In phase 2 (dose expansion), subjects who have not met any individual treatment discontinuation criteria and who are receiving clinical benefit (defined as achieving CRc or PR for AML and CR, BM CR, PR or HI for MDS, or other clinical benefits as determined by the investigator) will continue further treatment with ASP7517 after the first 2 cycles, as decided by the investigator.

After completing 4 cycles of treatment, subjects who achieve CR will not continue with ASP7517; subjects who do not reach CR, but also do not experience disease progression, may receive an additional 2 doses for a total of 6 doses.

Each cycle is defined as 28 days with a total of up to 6 treatment cycles.

An End-of-Treatment (EoT) visit will be conducted for all subjects within 7 days of the principal investigator decision to discontinue the subject from treatment or prior to the

initiation of new anticancer therapy, whichever occurs first. If a subject is completing all visits in the last treatment cycle, the EoT visit will be within 7 days from the last planned visit.

After the EoT visit, Observation Period 1 will be 12 weeks or until 1 post-treatment discontinuation criterion is met, whichever comes first. Subjects who achieve composite complete remission (CRc) or PR for AML and CR, bone marrow (BM) CR or PR or HI for MDS or other clinical benefits, as determined by the investigator, will remain in the study in Observation Period 2 until 1 post-treatment discontinuation criterion is met. Safety and efficacy will be monitored during Observation Periods 1 and 2.

Upon treatment or post-treatment discontinuation criterion is met and subjects discontinue from the Treatment Period, Observation Period 1, or Observation Period 2, all subjects will be followed for survival and subsequent anti-cancer treatments and outcomes by telephone calls every 3 months.

This study consists of 2 parts: phase 1 dose escalation and phase 2 dose expansion.

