- s. After the first 4 cycles of treatment, subjects who achieve CR will not continue with ASP7517; subjects who do not reach CR, but also do not experience disease progression, may receive an additional 2 doses for a total of 6 doses. If a participant experiences CR during cycle 5 or 6 (except if confirmed on day 1 of these cycles), the participant can complete the cycle and EoT will be performed as defined in footnote "o".
- t. Extramedullary disease assessment is required at screening, day 1 of every cycle starting with cycle 2, EoT, and observation visits.

Table 3 Schedule of Post-Treatment Period Assessments for Dose Escalation and Dose Expansion

Assessments	Post-Treatment Period							
	Observation Period 1						Observation Period 2	
	12 weeks or until 1 post-treatment discontinuation criterion is met						Until 1 post-treatment discontinuation criterion is met	
Visit Week	2	4	6	8	10	12	Monthly Safety Assessment Visit	Assessment Visit Every 3 months
Window (days)	± 3	± 3	± 3	± 3	± 3	± 3	± 3	± 3
Physical Examination ^a	X	X	X	X	X	X	X	X
Disease Assessment	X	X	X	X	X	X	X	X
Vital Signs	X	X	X	X	X	X	X	X
ECOG Performance	X	X	X	X	X	X	X	X
Concomitant Medications ⁱ	X	X	X	X	X	X	X	X
12-Lead ECG ^b	X	X	X	X	X	X	X	X
Clinical Laboratory Tests (chemistry, hematology, coagulation, urinalysis) ^g	X	X	X	X	X	X	X	X
Pregnancy Test for WOCBP	X	X	X	X	X	X	X	X
Bone Marrow Aspiration and/or Biopsy ^c						X ^h		X
Blood Sample for Disease Assessment ^d		X		X				X
AE/SAE Assessment ⁱ	X	X	X	X	X	X	X	X
Pharmacokinetic: Blood Sample for Cell Kinetics	See Table 5 for detailed sample time points							
Blood Sample for WT1 Expression		X		X		X ^j		X ^f
Blood Sample for Immune Response Biomarker (ELISpot)		X		X		X ^j		X ^e
Blood Sample for Immune Response Biomarker (Tetramer)		X		X		X ^j		X ^f
Blood Sample for Immune Cell Phenotyping		X		X		X ^j		X ^e
Blood Sample for Cytokines		X		X		X ^j		X ^e
Blood Sample for Anti-HLA Antibody		X		X		X ^j		X ^f

AE: adverse event; ECG: electrocardiogram; ECOG: Eastern Cooperative Oncology Group; ELISpot: enzyme-linked immunospot; HLA: human leukocyte antigen; IP: investigational product; SAE: serious adverse event; WOCBP: women of childbearing potential; WT1: Wilms' tumor 1 protein.

Footnotes continued on next page

- a. Height measurement performed only at screening.
- b. The 12-lead ECGs will be recorded as a single assessment (in triplicate if deemed necessary, at least 2 minutes apart per time point) and read locally.

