6.7 Criteria for Continuation of Treatment

ASP7517 will not be made available after conclusion of the study to subjects who are still receiving and benefitting from study treatment in countries where the product does not have marketing approval and is not commercially available. ASP7517 is given as a maximum of 6 doses (up to 2 doses in the escalation phase; up to 6 doses in the expansion phase).

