8.1.1 Discontinuation Criteria from Treatment for Individual Subject(s)

The reason for discontinuation from study treatment must be documented in the subject's medical records.

A subject must discontinue study treatment for any of the following reasons:

- Subject declines further study participation (i.e., withdrawal of consent).

- Any clinical or unacceptable AE/SAE, laboratory abnormality or intercurrent illness, in the opinion of the investigator, indicates continued treatment is not in the best interest of the subject.
- Subject is noncompliant with protocol based on the investigator or medical monitor assessment.
- Subject is found to have significantly deviated from any 1 of the inclusion or exclusion criteria after enrollment (subjects having clinical benefit and no DLT may be kept in the study after discussion with the medical monitor).
- Subject not achieving remission (CRc or PR in AML or CR, BM CR or PR or HI in MDS) and the subject is no longer deriving clinical benefit, in the opinion of the investigator.
- Subject begins other anti-leukemic therapies or MDS therapies, including undergoing HSCT.
- Subject experiences disease relapse/progression.
- Investigator/subinvestigator determines that the continuation of the study treatment will be detrimental to the subject.
- Subject is lost to follow-up despite reasonable efforts by the investigator to locate the subject.
- Female subject becomes pregnant.
- Death.
- Subject develops a grade 4 DLT during cycle 1.
- Delay of > 2 weeks of a subsequent scheduled dose of ASP7517 due to ASP7517-related toxicities.

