8.1.2 Discontinuation Criteria Post-Treatment for Individual Subject(s)

The reason for discontinuation from study post-treatment must be documented in the subject's medical records.

A subject must discontinue post-treatment for any of the following reasons:

- Subject declines further study participation (i.e., withdrawal of consent).
- Subject is lost to follow-up despite reasonable efforts by the investigator to locate the subject.
- Subject begins other anti-leukemic therapies or MDS therapies, including undergoing HSCT.
- Subject experiences disease relapse/progression.
- Subject is no longer deriving clinical benefit, in the opinion of the investigator.
- Female subject becomes pregnant.
- Death.

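### Subjects who stop ASP7517 for progression or lost benefit may have no scheduled adverse-event contact between the End-of-Treatment visit and day 30 after the last dose, although AE collection and the TEAE definition run to that day

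*Protocol*

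**What the plan says.** Protocol 4.1.1 gives every subject an EoT visit. It takes place "within 7 days of the principal investigator decision to discontinue the subject from treatment", or before new anticancer therapy if that comes first. For a subject who completes the last cycle, "the EoT visit will be within 7 days from the last planned visit". Neither rule refers to the date of the last dose.

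After EoT, "Observation Period 1 will be 12 weeks or until 1 post-treatment discontinuation criterion is met, whichever comes first". When a treatment or post-treatment criterion is met and the subject leaves the Treatment Period or either observation period, "all subjects will be followed for survival and subsequent anti-cancer treatments and outcomes by telephone calls every 3 months". The footnotes to the survival row (Table 1 footnote r, Table 2 footnote q) give the same content for these calls and include no AE item.

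Section 8.1.1 lists "Subject experiences disease relapse/progression" as a reason to stop treatment, and also loss of clinical benefit in a subject without remission. Section 8.1.2 repeats progression as a reason to leave post-treatment observation and adds "Subject is no longer deriving clinical benefit, in the opinion of the investigator".

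On safety, 7.3.1 and Table 3 footnote i extend AE collection to at least 30 days after the last dose, ending earlier if new anticancer treatment starts. Protocol 9.5.1 and SAP 5.2.3 define TEAEs to 30 days after the final dose. AE assessments are scheduled at treatment visits (Tables 1 and 2) and observation visits (Table 3). No table has a contact fixed at day 30 after the last dose.

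**The concern.** The obligation to collect AEs to day 30 is clear, but for one group of subjects the schedules may not provide the contact needed to meet it. A subject who stops for progression or lost benefit has, at that moment, already met a criterion that ends Observation Period 1. The next contact would then be a call about three months later that does not ask about AEs.

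Safety and tolerability are a primary objective of this first-in-human trial. SAP 5.2.3 counts AEs that were collected and began within the window, while every treated subject stays in the safety analysis set. Events that nobody asks about are therefore missing from the numerator only. Protocol 2.1.2.1.5 names fever, headache, fatigue, diarrhea and joint pain among possible immune-related reactions, and SAP 6.5.2 tabulates immune-related AEs as events of special interest. A telephone call can pick up such symptoms.

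**Working it through.** The plan states no figure for this point, so the check is a comparison of sections followed by day counting.

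**Routing.** Progression and lost benefit appear in both 8.1.1 and 8.1.2. Section 4.1.1 runs Observation Period 1 only until a criterion in 8.1.2 is met, and it names leaving the Treatment Period as a route to the 3-monthly calls. Taken together, these subjects go from EoT to the calls.

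**Inputs.** The last dose is on day 1 of a cycle. The window ends 30 days later, on day 1 + 30 = day 31. EoT falls 0 to 7 days after the stop decision or the last planned visit (4.1.1). Nominal visit days are used, and EoT is taken to be an AE contact.

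**Formula.** Gap = max(0, 31 - EoT day).

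| Stop decision or last planned visit | EoT day | Days without a scheduled AE contact |
|---|---|---|
| Day 8 | 8 to 15 | 31 - 15 = 16 to 31 - 8 = 23 |
| Day 15 | 15 to 22 | 31 - 22 = 9 to 31 - 15 = 16 |
| Day 22 | 22 to 29 | 31 - 29 = 2 to 31 - 22 = 9 |
| Next cycle's day 1 (day 29) | 29 to 36 | 0 to 31 - 29 = 2 |

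**First survival call.** If it comes about 91 days (+/-3) after EoT, which is an assumption, then even an EoT on day 8 (7 days after the dose) puts it at 7 + 91 - 3 = 95 days after the dose, well beyond 30.

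**Can this happen on the planned path?** Yes, in each phase's final cycle. Dosing is limited to "up to 2 doses in the escalation phase; up to 6 doses in the expansion phase", so no day-1 assessment follows phase 1 cycle 2 or phase 2 cycle 6. Disease is assessed at EoT in both phases; for phase 2, Table 2 footnote t reads "Extramedullary disease assessment is required at screening, day 1 of every cycle starting with cycle 2, EoT, and observation visits". If progression is first found at that EoT, the last planned visit is day 22 in phase 1 cycle 2 (gap 2-9 days) and day 15 in phase 2 cycle 6 (gap 9-16 days).

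**If the subject does enter Observation Period 1 and leaves at week 2.** That visit falls on EoT + 14, +/-3 days:
- Day-8 decision: day 8 + 11 = 19 to day 15 + 17 = 32, so the gap is 0 to 31 - 19 = 12 days.
- Day-15 decision or last visit: day 15 + 11 = 26 to day 22 + 17 = 39, so the gap is 0 to 31 - 26 = 5 days.
- Day 22 or later: the earliest visit is day 22 + 11 = 33, so there is no gap.

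A week-4 visit cannot fall before day 8 + 28 - 3 = 33, which is past the window.

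**The case against.** The strongest objection is that the routing is inferred. No sentence says that progressors skip Observation Period 1, and the flow chart in Figure 2 is not shown in the public text. Section 8.2 keeps everyone who stops treatment in protocol follow-up, cites Table 3, and allows withdrawal of consent as the only exception. Section 4.1.1 makes entry to Observation Period 2, but not Period 1, depend on response or benefit. Table 3 footnote h expects a marrow sample at the last Period 1 visit from subjects who will not go on to Period 2, so at least some non-responders are expected there. Read literally, the 4.1.1 sentence would also send every toxicity stop straight to calls. This stands as a real ambiguity. It does not remove the problem: 8.2 only points back to 4.1 and the same tables, and a subject who leaves at week 2 can still fall up to 12 days short.

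Second, 7.3.1 already states the duty, and 7.3.2 prefers open verbal questioning, so a careful site would make contact unprompted. That is correct, and a reader should not infer that the plan fails to require day-30 collection. What is missing is a scheduled contact with which to meet the requirement.

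Third, routine marrow and disease assessment falls on the next cycle's day 1, where the gap is only 0-2 days. The longer gaps need a stop at another time or at the end of a final cycle. This also stands, and the documents give no distribution of stop days.

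**Conclusion.** The point holds as a scheduling gap on the most natural reading of 4.1.1, 8.1.1 and 8.1.2: 0-2, 2-9, 9-16 or 16-23 days according to when treatment stops, or 0-12 days if the subject attends week 2 of Observation Period 1 and leaves there. These figures assume nominal visit days and an EoT visit that includes AE assessment.

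The likely loss is confined to non-serious AEs, and serious AEs not judged related, late in the window. Deaths to day 30 (7.3.5), related serious AEs (7.3.1) and related events the investigator learns of later (7.3.3) are still captured. For a subject who starts new anticancer therapy, general AE collection ends by design.

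Two stronger readings are tempting. One is that TEAE rates are biased downward. The documents support only that TEAE and immune-related AE rates may be understated, by an unknown amount, unless sites make unscheduled contact. The other is that dose or stopping decisions are compromised. Phase 2 safety stopping uses DLTs and drug-related fatal TEAEs, and nothing here shows that a DLT count or a stopping decision would change. This is a worthwhile low-cost improvement, not a defect in the safety analysis itself.

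**What to change.** Amend Protocol 4.1.1, the matching synopsis and SAP 2.2 text, and the survival follow-up rows of Tables 1, 2, 13 and 14. For any subject whose last scheduled AE contact (EoT or an observation visit) falls before day 30 after the last dose, time the first telephone contact at day 30, plus a few days. Ask about AEs, serious AEs and new therapy, and limit general AE questions to the time before any new therapy. Later calls stay every 3 months. Because the rule depends on the last scheduled AE contact, it works whichever way the Observation Period 1 routing is meant. The crisis schedule in Table 14 already accepts AE assessment by telephone at non-dosing visits.

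The cost is one earlier call per affected subject by existing site staff, with AE questions added and no extra visit or procedure. It adds little for a stop at the next cycle's day 1 and is not needed when an observation visit already falls on or after day 30. A call recovers symptomatic or reported events only. It does not detect laboratory-defined events such as liver enzyme or neutrophil changes, and should not be presented as doing so.

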4.1.2 Phase 1 Dose Escalation

The dose escalation portion will assess safety and tolerability of ASP7517. In the dose escalation phase, subjects must be managed under hospitalization for at least 7 days during the first cycle of the dose escalation phase. In addition, prior to hospital discharge, the investigator must ensure subject safety by performing medical tests and procedures listed on day 7 of cycle 1 and tests considered clinically necessary in the opinion of the investigator to evaluate the subject's general condition and AE resolution. The subject should also be followed on an outpatient basis on planned visits during cycle 1 and 2 after hospital discharge during the DLT assessment period to closely monitor any AEs. Subjects may be hospitalized days 1 to 7 during cycle 2 based on investigator opinion.

After dosing of ASP7517, subjects must be observed for safety for a minimum of 4 hours. The safety observation will consist of hourly vital signs and AE observations. If new AEs are observed that are \geq grade 3 during this time, subjects should continue to be observed at the investigator's discretion.

In phase 1 (dose escalation), the starting dose level is 1×10^6 cells/dose and the decision to dose escalate to the next dose levels (1×10^7 and 1×10^8 cells/dose) will be made based on the assessment of safety variables, including the occurrence of dose limiting toxicities (DLTs). Dose escalation will be guided according to the Bayesian optimal interval (BOIN) design [Liu et al, 2015] to determine the next dose level based on DLT occurrence. After the planned number of evaluable subjects have completed the DLT observation period for a given dose level, safety for that dose level will be assessed. Each dose level in the dose escalation phase will enroll a minimum of 3 and may enroll a maximum of 8 subjects with up to 4 evaluable subjects for the initial assessment of each dose level. Enrollment within each dose escalation cohort will be staggered such that there will be 28 calendar days between the treatment initiation of the first subject and the second subject, as well as 14 calendar days between the second subject and the third subject at the same dose level for all escalation cohorts. An interval of 28 calendar days will separate initiation of first dose of study

treatment for the last subject in a dose cohort from the first subject in the subsequent dose cohort. The 28-day separation is equivalent to the 28-DLT evaluation period. If the decision is made to stay at the current dose level, then an additional 3 or 4 evaluable subjects may be enrolled to the current dose level. Three to 18 subjects will be enrolled in the dose escalation phase. A minimum number of 6 subjects and a maximum number of 8 subjects must be enrolled at the dose level used to determine the maximum tolerated dose (MTD) and the recommended phase 2 dose (RP2D).

Safety data and other available clinical data will be reviewed on an ongoing basis to determine if the study will proceed to the next dose level/phase.

Subject Replacement during Dose Escalation:

Subjects may be replaced in the dose escalation cohort if:

- Subject is discovered to have enrolled without fully satisfying eligibility criteria.
- Subject received less than the planned dose in cycle 1 for reasons other than DLT.
- Subject has no DLT and withdraws from the study before the end of the DLT evaluation period.

The decision regarding replacement of individual subjects will be made by the sponsor with discussions with the treating investigator.

